  - Post-dose systolic blood pressure of  $\geq 200$  mmHg and/or the DBP is  $\geq 120$  mmHg confirmed by triplicate reading (at least one value should confirm the blood pressure increase above the defined thresholds).

If discontinuation of study treatment occurs, the investigator should make a reasonable effort to understand and record the primary reason for the participant's premature discontinuation of study treatment.

Participants who discontinue study treatment or who decide they do not wish to participate in the study further should NOT be considered withdrawn from the study UNLESS they withdraw their consent (see [Section 9.1.2](#)). Where possible, they should return for the assessments indicated in the Assessment Schedule. If they fail to return for these assessments for unknown reasons, every effort (e.g. telephone, e-mail, letter) should be made to contact the participant/pre-designated contact as specified in the lost to follow-up section.

If the participant cannot or is unwilling to attend any visit(s), the site staff should maintain regular telephone contact with the participant, or with a person pre-designated by the participant. This telephone contact should preferably be done according to the study visit schedule.

Following study treatment discontinuation (no further infusions planned), participants should be followed for two months beyond the 6 week Core Period (Follow-up Period).

Participants who discontinue study treatment during the Core Period should return at every scheduled visit until the End of the 6 week Core Period. The list of assessments should be kept as planned with the following exceptions: ECG and vital signs to be measured (triplicates required), no PK sampling collection, and all assessments that are repeated several times in one day should be done only once [REDACTED]

[REDACTED] Participants will then enter the two months Follow-up Period.

Participants who discontinue study retreatment during the Extension Period should return for the End of Relapse visit and subsequently enter the two month Follow-up Period.

If an onsite visit is not possible, then telephone visits should be conducted and collected at minimum the following:

- New / concomitant treatments
- Adverse Events / Serious Adverse Events

The investigator must also contact the IRT to register the participant's discontinuation from study treatment.

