Period	Screening	Core Period																		
Visit Name	Screening	Day 1 (1st infusion)							Day 2	Day 8	Day 15 (2nd infusion)						Day 22	Day 29 (3rd infusion)		
Days	-2 to -1	1							2	8	15						22	29		
Time (post-dose)	-	-2h ±1 	- 1h	0h	20min	40min	2h	4h	24h	-	-2h ±1	- 1h	0h	40min	2h	4h	-	-2h ±1	- 1h	0h
MADRS	Last 7 days with euthymic baseline	Last 7 days						Since infusion start (last 4 hrs)	Since last evaluation	Last 7 days	Last 7 days					Since infusion start (last 4 hrs)	Last 7 days	Last 7 days		

Period	Core Period				Extension			End of Study	
Visit Name	Day 29 (3rd infusion)			Day 36	End of Core	2 weeks F/U 	4 weeks F/U 	Every 4 weeks 	End of Study
Days	29			36	43	57	71	99	-
Time (post-dose)	40min	2h	4h	-	-	-	-	-	-

Period	Retreatment for relapse																			
Visit Name	Pre-retreatment	Day 1 (1st infusion)						Day 2	Day 8	Day 15 (2nd infusion)						Day 22	Day 29 (3rd infusion)			
Days	-14 to -1	1						2	8	15						22	29			
Time (post-dose)	-	-2h ±1	- 1h	0h	40min	2h	4h	24h	-	-2h ±1	- 1h	0h	40min	2h	4h	-	-2h ±1	- 1h	0h	40min
MADRS	Last 7 days	Last 7 days with euthymic baseline					Since infusion start (last 4 hrs)	Since last evaluation	Last 7 days	Last 7 days					Since infusion start (last 4 hrs)	Last 7 days	Last 7 days			

Period	Retreatment for relapse																		
Visit Name	Pre-retreatment	Day 1 (1st infusion)						Day 2	Day 8	Day 15 (2nd infusion)						Day 22	Day 29 (3rd infusion)		
Days	-14 to -1	1						2	8	15						22	29		
Time (post-dose)	-	-2h ±1h	0h	40min	2h	4h	24h	-	-2h ±1h	0h	40min	2h	4h	-	-2h ±1h	0h	40min		

Period	Retreatment for relapse			
Visit Name	Day 29 (3rd infusion)		Day 36	End of Retreatment
Days	29		36	43
Time (post-dose)	2h	4h	-	-
MADRS		Since infusion start (last 4 hrs)	Last 7 days	Last 7 days

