2.1.2 Analysis period and visit remapping

All study data of participants will be grouped into Core Period and Extension Period according to [Table 2-1](#). For those who take retreatment for relapse, assessments during retreatment will be grouped into Retreatment Period specially.

Table 2-1 Analysis Period for Data

Analysis Period	Start Time Point	End Time Point
Core Period	Day 1	For participant who won't join in Extension Period: Date of End of study visit; For participant who join in Extension Period: End of Core visit (Day 43)
Extension Period	For participant who join in Extension Period: Date of End of Core visit + 1	For participant who join in Extension Period: Date of End of Study visit
Retreatment Period	For participant who take retreatment: Date of first dose of retreatment	For participant who take retreatment: Date of last Retreatment visit

Analysis visit and windows

Since the actual visit for a participant may not exactly coincide with their targeted visit date, the actual visit date will be mapped to an analysis visit for the purpose of data summary and model analysis. However for assessments (except for PK sampling) performed at -2 hours, -1 hour, 20 min, 40 min, 2 hours, 4 hours on the same day, there is no need to remap visit time, so site collected timepoint will be analysed.

The visit window in [Table 2-2](#) defines the analysis visit applicable for assessments in Core Period and Extension Period, including efficacy endpoints (e.g. MADRS, [REDACTED]), safety endpoints (e.g. laboratory, vital signs, ECG, [REDACTED]).

Table 2-2 Analysis Visit Windows for Core Period and Extension Period

Analysis Period	Study Visit	Target Day/Time	Study Day
Core Period	Baseline	Day 1 -2 hours predose (See definition for baseline in Section 2.1.1)	-2, - 1, 1 (predose)
	D1 20 min, 40 min, 2 h, 4 h	Day 1 20 min, 40 min, 2 hours, 4 hours post dose	1 (post dose)
	24 h	2	2
	D8	8	3 - 11
	D15 -2 h, -1 h, 40 min, 2 h, 4 h	Day 15 -2 hours, -1 hour predose, 40 min, 2 hours, 4 hours post dose	12 - 18
	D22	22	19 - 25
	D29 -2 h, -1 h, 40 min, 2 h, 4 h	Day 29 -2 hours, -1 hour predose, 40 min, 2 hours, 4 hours post dose	26 - 32
	D36	36	33 - 39
	D43	43	40 – End of Core Visit
Extension Period	2 weeks follow-up	57	(End of Core Visit + 1) - 64
	4 weeks follow-up	71	65 - 85
	Monthly follow-up post Day 43	43 + (n)*28 n is the nth month follow up	(-13, +14) of target day The last follow-up visit will last until the end of study

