The main analyses will summarize data collected in Core Period up to 2 weeks follow up in Extension Period. The monthly follow-up visit in Extension Period will not be presented in by-visit summary, unless otherwise specified.

In addition for participants who are retreated during Extension Period, assessments performed during Retreatment Period will be mapped to the analysis visit according to [Table 2-3](#).

Table 2-3 Analysis Visit Windows for Retreatment Period

Analysis Period	Study visit	Target Day since start of retreatment*	Day since start of retreatment*
Retreatment Period	Baseline of Retreatment	Day 1 -2 hours pre-retreatment (See definition for	1

		baseline of retreatment in Section 2.1.1)	
	Retreatment D1 40 min, 2 h, 4 h	Day 1 40 min, 2 hours, 4 hours post retreatment	1
	Retreatment 24 h	2	2
	Retreatment D8	8	3 - 11
	Retreatment D15 -2 h, -1 h, 40 min, 2 h, 4 h	Day 15 -2 hours, -1 hour predose, 40 min, 2 hours, 4 hours post dose	12 - 18
	Retreatment D22	22	19 - 25
	Retreatment D29 -2 h, -1 h, 40 min, 2 h, 4 h	Day 29 -2 hours, -1 hour predose, 40 min, 2 hours, 4 hours post dose	26 - 32
	Retreatment D36	36	33 - 39
	Retreatment D43	43	40 – End of Retreatment Visit

* See the definition for Day(s) since start of retreatment in [Section 2.1.1](#)

When multiple assessments are mapped into the same window, following rules will be applied for efficacy and safety endpoints (except ECG) and PROs:

When assessments for scheduled visit and unscheduled visit are both present within the same window, the scheduled assessments value should be used. Unscheduled visit will only be used when there is no measurement from the scheduled visit in the defined window. Two special cases need to be handled as following rule:

- When assessments on a dosing day drop to the window of a non-dosing visit, for example the dosing on Day 15 was delayed to the window of Day 22, the pre-dose assessment will be mapped to the non-dosing visit of Day 22, while the post-dose assessment will not be mapped. Unless scheduled assessments for Day 22 were performed, the scheduled ones should be mapped then.
- When assessments on non-dosing day drop to the window of a dosing visit, for example the visit Day 8 was delayed to Day 15 and no dosing was administered, assessments will be mapped to the pre-dose hour of this dosing visit. Unless the dosing were administered and scheduled assessments performed within the window, the scheduled assessments should be mapped then.

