2.5.1 Secondary endpoints

To assess the effect of MIJ821 on sustained response and remission, following secondary efficacy endpoints will be evaluated:

- Proportion of participants meeting response criteria ($\geq 50\%$ reduction from baseline in MADRS total score) over time in the Core Period.
 - Participants who do not meet the criterion or discontinue Core Period prior to the time point due to any reason or with missing score (baseline and/or post baseline) will not be considered as "a responder" at that timepoint.
- Proportion of participants meeting criteria for sustained response ($\geq 50\%$ reduction from baseline in MADRS total score sustained for a period of at least four weeks) in the Core Period

- The sustained response ideally requires all scheduled assessments over four weeks achieving 50% reduction from baseline. However, if there is one or more missing assessment(s) between two responses, the response will be assumed to be sustained over missing assessment(s), unless other specified. For example, one participant observed a response at Day 1 4 hours, Day 29 -2 hours, however missed the assessment at 24 hours, Day 8, Day 15 and Day 22, this participant is still considered as meeting the sustained response. The missing due to study discontinuation will not be imputed. Participants who do not meet the criterion will not be considered as “a responder” at the timepoint.
- Proportion of participants meeting remission criteria (MADRS total score of ≤ 12) over time in Core Period
 - Participants who do not meet the criterion or discontinue prior to the time point due to any reason or with missing score (either at baseline or post baseline) will not be considered as “a remitter” at that timepoint.
- Proportion of participants meeting criteria for sustained remission (MADRS total score of ≤ 12 sustained for a period of at least four weeks) in the Core Period
 - The rule for sustained remission is the similar with sustained response. Participants who do not meet the criterion will not be considered as “a remitter” at the timepoint.
- Proportion of participants meeting criteria for relapse over fixed period in the Extension Period
 - The definition and criteria of relapse could be referred to protocol section 3.4. The relapse will be evaluated by investigator and reported in the CRF form “Relapse and re-treatment criteria”. Participants without relapse reported will not be counted.

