2.5.2 Statistical hypothesis, model, and method of analysis

Analysis of above secondary efficacy endpoints will be based on FAS (Core Period) or RTS (Retreatment Period), except the following endpoints:

- Proportion of participants meeting criteria for relapse over fixed period in the Extension Period will be based on ENS
- Proportion of relapsing participants meeting response criteria or remission criteria after the first infusion of MIJ821 retreatment in the Extension Period will be based on RTS

No hypothesis will be tested for the secondary efficacy endpoints.

Frequency tables (count and proportion) will be provided for these endpoints by analysis visit after imputation for missing values. Details on missing data handling are described in [Section 2.5.1](#). Bar chart will be plotted by treatment arm and analysis visit.

The proportion of participants meeting criteria for relapse over 1 month, 2 months, 3 months, 6 months 9 months and 12 months in Extension Period will be plotted for each treatment arm based on ENS for responders/remitters at EoC visit. In addition for responders/remitters, the time to first relapse will be analyzed by kaplan-meier (KM) method and display in KM plots. The median time to first relapse will be summarized with 90% CI.

If data warranted, the treatment differences of each MIJ821 dose versus Placebo will be analyzed separately, using a repeated logistic regression model, for following endpoints:

- Proportion of participants meeting response criteria ($\geq 50\%$ reduction from baseline in MADRS total score) over time in the Core Period.
- Proportion of participants meeting criteria for sustained response ($\geq 50\%$ reduction from baseline in MADRS total score sustained for a period of at least four weeks) in the Core Period
- Proportion of participants meeting remission criteria (MADRS total score of ≤ 12) over time in Core Period
- Proportion of participants meeting criteria for sustained remission (MADRS total score of ≤ 12 sustained for a period of at least four weeks) in the Core Period

For response rate and remission rate per visit, the repeated logistic regression model will be established with the fixed, categorical effects of treatment (6 dose arms and 1 placebo arm), time, treatment*time interaction, region, the fixed continuous baseline MADRS score, and baseline score*time interaction. [REDACTED]

[REDACTED]

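### Participants off study drug have one MADRS on Day 15 and Day 29, but the SAP has two analysis slots on each day and scores the empty one as non-response and non-remission

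*SAP*

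**What the plan says.** Protocol 9.1.1 keeps people in the study after they stop drug: "Participants who discontinue study treatment during the Core Period should return at every scheduled visit until the End of the 6 week Core Period". It lightens those visits: "all assessments that are repeated several times in one day should be done only once". The text that follows this sentence is redacted.

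MADRS is one of the repeated assessments. Protocol Appendix 6 schedules it before dosing, with a seven-day recall, and again at 4 h, with a recall that runs from the start of the infusion. SAP 2.4.1.1 also describes a 4 h MADRS on the dosing days (it prints Day 25 for the third, apparently Day 29).

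SAP 2.1.2 sets the analysis slots. The Day 15 row of Table 2-2 reads "D15 -2 h, -1 h, 40 min, 2 h, 4 h", and the Day 29 row has the same pattern. For a non-dosing assessment that falls in a dosing-visit window, where "no dosing was administered, assessments will be mapped to the pre-dose hour of this dosing visit", the value takes the pre-dose slot. The same section says that, for the within-day time points, the time point recorded by the site is analysed.

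SAP 2.5.1 says that a participant "with missing score (baseline and/or post baseline) will not be considered as" a responder at the time point concerned, with a parallel rule for remission. SAP 2.5.2 bases the Core endpoints on the FAS and states: "Frequency tables (count and proportion) will be provided for these endpoints by analysis visit after imputation for missing values". If the data warrant it, a repeated logistic model with treatment, time and their interaction is also fitted.

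**The concern.** Each rule is reasonable alone; together they misclassify people. Someone who stopped drug, attends Day 15 and meets the 50% criterion gives one score. That score makes them a responder in one slot, and the rule makes them a non-responder in the other slot of the same day. The second score was never due, so it is not a lost observation.

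At the affected slot, response and remission over time therefore measure partly whether an infusion was given. A by-visit table or bar chart could show the rate changing within one day with no change in anyone's depression. Where the proportion off drug, or response among those off drug, differs by arm, the comparison with placebo moves too. Adverse events and lack of effect are both listed reasons for stopping in Protocol 9.1.1, so differences between arms are plausible.

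**Working it through.** The documents give no response rate and no treatment-discontinuation rate, so there is no stated figure to reproduce. The check is a trace of the rules followed by a formula.

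**Trace, for one participant off drug who is seen on Day 15**

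1. Still in the Core and due at the visit: yes (Protocol 9.1.1).
2. Still in the denominator: yes. The FAS needs one dose only (SAP 2.1.3).
3. Number of MADRS that day: one instead of two (Protocol 9.1.1 with Appendix 6).
4. Number of slots: two that matter, pre-dose and 4 h (Table 2-2). The SAP uses both kinds for response: its worked example in 2.5.1 counts a response at Day 1 4 h and one at Day 29 pre-dose.
5. Filled slot: pre-dose, if the no-dosing mapping rule applies; 4 h, if the site labels the score 4 h and that label is used.
6. Empty slot: scored as non-response and non-remission (SAP 2.5.1). No readable text exempts a score that was not due.

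Day 29 works the same way. Day 1 4 h does not, because everyone in the FAS had the first infusion.

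**Size at the empty slot**

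Let d be the share of an arm off drug but attending, p the response rate among those infused, and q the response rate among those not infused.

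- Rate at the filled slot: p(1 − d) + qd
- Rate at the empty slot: p(1 − d)
- Loss: qd

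All values below are assumptions, with p = 50%.

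| d | q = 0 | q = 25% | q = 50% |
|---|---|---|---|
| 5% | 0 | 1.25 points | 2.5 points |
| 10% | 0 | 2.5 points | 5 points |
| 20% | 0 | 5 points | 10 points |

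Over d = 5–20% and q = 30–60%, the loss runs from 0.05 × 0.30 = 1.5 points to 0.20 × 0.60 = 12 points. The 10% in the sample-size section is study dropout, not treatment discontinuation, so it does not supply d.

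**Effect on an arm difference**

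The shift in active minus placebo is −(q_A d_A − q_P d_P). With p = q = 50% in both arms:

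- d = 5% on placebo and 15% on active: 47.5% against 42.5%, a spurious −5 points.
- d = 5% and 20%: 47.5% against 40%, −7.5 points.
- d = 15% on placebo and 5% on active: +5 points.

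For scale, with 30 per arm and a rate of 50%, the standard error of a difference is √(2 × 0.25/30) = 12.9 points. The shifts of 5 and 7.5 points are about 0.4 and 0.6 of it.

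**The case against.** **Redacted text.** The once-only sentence runs into redacted text, and parts of SAP 2.5 are redacted too. An exception could sit there. This stands as a limit: the point rests on the readable text.

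**Which slot is empty.** The mapping example in SAP 2.1.2 is a delayed Day 8 visit, and the site-recorded time point is used within a day. A reader might infer that the 4 h rate is always the one lowered. The documents do not settle that. A score labelled 4 h moves the blank to pre-dose; it does not remove it.

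**Skipped infusions.** A reader might extend this to anyone who misses only the Day 15 infusion. SAP 2.2.1 does not count that as treatment discontinuation, and the once-only rule is written for those who discontinue. Whether such participants have one MADRS or two is not stated.

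**Off drug as failure by design.** A composite strategy could be defended, but the SAP does not adopt one. SAP 2.5 defines no secondary estimand, the rule in 2.5.1 refers to leaving the Core Period rather than stopping treatment, and the same person can be a responder in the other slot that day.

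**Conflict with sustained response.** That rule bridges gaps between two observed responses. It could be read as scoring the same blank in the opposite way, but it belongs to a different endpoint and is not a contradiction.

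**Little at stake.** Much of this stands. SAP 2.5.2 tests no hypothesis on these endpoints, and the logistic model is conditional on the data. The MMRM in SAP 2.4.6 uses original measurements, and listings flag response at each assessment, so a same-day change could be traced.

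**Conclusion.** The point holds on the readable text. For participants off drug who stay in the Core, one of two same-day slots on Day 15 and Day 29 is empty by design and scored as failure. The rule can only lower the rate at that slot, by (share off drug) × (share of them responding). The size is wholly assumed: 5 points at 10% and 50%, and nothing if no off-drug participant responds, which is possible because lack of effect is a reason to stop.

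Two stronger conclusions are not supported. A reader might infer a bias against the active or higher-dose arms; the direction is not guaranteed, because stopping for adverse events and stopping for lack of effect can pull opposite ways. A reader might also infer that the interim dose choice is compromised. SAP 2.11 bases it on the MCP-Mod dose response, sustained efficacy, safety and PK, and sustained response and remission largely bridge these blanks, so the influence is weak.

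The primary 24 h endpoint, Day 1 4 h and the MMRM are unaffected. This is an estimation and display fault in two secondary endpoints, worth correcting because the correction is cheap.

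**What to change.** - **SAP 2.1.2:** state that the single same-day score of a participant not infused is always mapped to the pre-dose slot.
- **SAP 2.5.1:** score a missing value as non-response or non-remission only at time points where the protocol made a score due for that participant.
- **SAP 2.5.2:** run the FAS by-visit comparison and the repeated logistic model on Day 1 4 h, 24 h, Day 8, Day 15 pre-dose, Day 22, Day 29 pre-dose, Day 36 and Day 43. Show Day 15 4 h and Day 29 4 h response and remission descriptively among those infused at that visit, with n, labelled as a post-randomisation subset not meant for comparison between arms.

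The cost is a few sentences in the SAP and a programming filter. The two later 4 h time points lose their model-based estimates. The infused subset may also favour people who respond to and tolerate treatment, which is why the label matters.

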### SoC can be adjusted or modified after the relapse retreatment, as clinically warranted. Extension Follow-up Duration

[figure not shown]
All participants must complete a follow-up period after the End of Core Period visit (Day 43):

- For participants who are neither remitters nor responders at the End of Core Period (Day 43) [Section 3.2](#), the follow up will last 8 weeks and consists of 3 mandatory visits (the 2 weeks Follow-up visit, the 4 weeks Follow up visit and the End of Study visit occurring 8 weeks after Day 43)
- For participants who are responders or remitters at the End of the Core Period (Day 43), and who do not experience any relapse, the Extension Period will last 52 weeks. This will consist of the 2 weeks Follow-up visit, the 4 weeks Follow-up visit, and thereafter Follow-up visits occurring every 4 weeks up to End of Study visit at Week 52
- Participants who are responders or remitters at the End of the Core Period (Day 43), and who relapse during the Extension Period, will receive one course of retreatment with MIJ821.
  - After that course of retreatment:
    - The participant will resume the 4 weekly Follow-up visit schedule (E.g., if the 6 weeks relapse retreatment period occurred from week 19 to 25, the participant will not perform visits week 20 and week 24, and will resume the follow-up at week 28).

- The duration of the follow up will be as per the initial schedule up to Week 52 or clinical worsening, whichever comes first, but they must complete at least 8 weeks follow-up period (see [Section 6.1.4](#)). Signs of clinical worsening may include worsening of depressive mood, need for SoC adjustments, a suicidal attempt, hospitalization for depression or suicidal ideation or behavior. For patient management see [Section 3.4](#), subsection Relapse and Clinical Worsening.
- Participants who are responders or remitters at the End of the Core Period (Day 43), and who relapse during the Extension Period but do not meet the weight requirements of 50-120kg (inclusive), cannot be retreated for the relapse and must be discontinued. The Extension period for these participants should last at least 8 weeks before the discontinuation.

The total duration of the Extension Period is 52 weeks, maximum. Therefore, the last date of confirmed relapse enabling access to the retreatment period is 38 weeks. If a participant relapses on or after that date, the participant must complete the End of Study visit as soon as possible.

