2.1.3 Analysis sets

The Randomized Set (RAS) consists of all randomized participants. The descriptions of population will be based on RAS.

The Full Analysis Set (FAS) comprises all randomized participants who received at least one dose of randomized study treatment. Participants will be analyzed according to the treatment they have been assigned to during the randomization procedure. The primary efficacy analysis for data in Core Period will utilize this analysis set.

The Safety Set (SAF) includes all participants who received at least one dose of study treatment. Participants will be analyzed according to the treatment received. In case participants take the wrong treatment (different with the assigned treatment), the first treatment received will be used in analysis. Safety analysis for data in Core Period will be based on SAF.

The Extension Set (ENS) is defined to include all subjects who joined Extension Period. Data collected during follow-up period will be analyzed based on ENS, and grouped by the assigned treatment in Core Period. In case participants take the wrong treatment during Core, the first actual treatment taken will be used for the analysis of safety data only. The analysis of data collected during extension period (before and after re-treatment period) will be based on ENS.

The Retreatment Set (RTS) is defined as a subset of SAF including participants who received at least one dose for the retreatment of relapse. Participants will be analyzed according to the treatment received for the first injection during the Retreatment Period. The efficacy and safety endpoints pertinent to Retreatment Period (see [Table 2-1](#)) will be analyzed based on RTS.

PK Analysis Set (PKS) includes all participants who provided at least one evaluable PK concentration. Determined PK concentrations may be excluded from the PKS (per the scientific judgement of the PK scientist, e.g. non-plausible concentrations). All subjects within the PK analysis set will be included in the PK data analysis. PK samples from subjects treated with MJJ821 will be measured and PK samples from placebo treated subjects will not be measured.

[REDACTED]

[REDACTED]

[REDACTED]

[REDACTED]

[REDACTED]

[REDACTED]

[REDACTED]

[illegible]

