- Proportion of relapsing participants meeting response criteria or remission criteria after the first infusion of MIJ821 retreatment in the Extension Period
 - After the retreatment, the proportion of participants meeting response or remission criteria again will be derived based on all relapsing participants who have achieved response or remission at the end of Core Period.

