5.2 Rule of exclusion criteria of analysis sets

Table 5-2 Subject Classification

Analysis Set	PD ID that cause participants to be excluded	Non-PD criteria that cause participants to be excluded
FAS	NA	Not randomized No double-blind study drug taken
SAF	NA	No double-blind study drug taken
ENS	NA	Not enter into extension phase
RTS	NA	No retreatment administered No relapse observed None of responder or remitter
PKS	NA	Input from PK scientist

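### The SAP gives two denominators for the descriptive retreatment-success endpoint, and they differ because the protocol bars some relapsers from retreatment

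*SAP*

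**What the plan says.** The endpoint is the proportion of relapsing participants who meet response or remission criteria after the first retreatment infusion.

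- **SAP 2.5.1:** the proportion "will be derived based on all relapsing participants who have achieved response or remission at the end of Core Period".
- **SAP 2.5.2:** the proportion "after the first infusion of MIJ821 retreatment in the Extension Period will be based on RTS".
- **SAP 2.1.3:** the RTS is a "subset of SAF including participants who received at least one dose for the retreatment of relapse", grouped by the treatment received at the first retreatment infusion.
- **SAP Table 5-2:** the RTS exclusions are "No retreatment administered No relapse observed None of responder or remitter".
- **Protocol 3.3, Extension Follow-up Duration:** "The total duration of the Extension Period is 52 weeks, maximum", and "the last date of confirmed relapse enabling access to the retreatment period is 38 weeks". For later relapses, "If a participant relapses on or after that date, the participant must complete the End of Study visit as soon as possible". Relapsers outside 50-120 kg are not retreated either.
- **Protocol 8.4.4:** a participant who is pregnant at relapse is not retreated.

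SAP 2.5.2 refers to 2.5.1 for missing data. There, the per-visit response and remission endpoints each have a rule that a missing score does not count as success. The retreatment endpoint has no such rule. SAP 2.5.3 adds only that values missing through discontinuation are not imputed. SAP section 4 records no change from the protocol.

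**The concern.** The endpoint asks whether the drug works again when it is given for a relapse. A relapser who is never dosed has no score after a retreatment infusion and cannot enter the numerator. If such a person stays in the denominator, the proportion partly measures when the relapse came, body weight and pregnancy, rather than the effect of retreatment. An arm whose relapses come later would lose more. As written, the programmer has to choose between the two sections, and the choice could be made with unblinded data in hand.

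Table 5-2 raises a related, smaller problem. SAP 2.1.3 admits anyone dosed for retreatment of relapse. Table 5-2 also lists the absence of relapse, and not being a responder or remitter, as exclusions. In the FAS row of that table each criterion excludes on its own. Read the same way, the RTS row drops a participant who was dosed without meeting the criteria. SAP 2.6 and 2.6.1 base the retreatment safety tables on the RTS, so an exposed participant could disappear from them.

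**Working it through.** **The plan's own figure.** The week-38 limit reproduces from the 52-week extension, the 6-week retreatment course and the minimum 8-week follow-up: 52 − 6 − 8 = 38.

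**Direction (no assumed figures).** Let x be the number of successes, m the number retreated and u the number of relapsing end-of-Core responders or remitters who are not retreated. The RTS rate is x/m and the literal 2.5.1 rate is x/(m + u). Since u ≥ 0, the second cannot exceed the first. This takes everyone retreated to be a relapsing responder or remitter, as the protocol requires.

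**Size (assumptions needed).** The documents give no 52-week relapse risk R, relapse timing, Day 43 response rate or retreatment success rate p. With a Weibull shape k for relapse timing:

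- S(t) = (1 − R)^((t/52)^k)
- share of relapses after week 38: f = [S(38) − S(52)] / R
- shift in the rate = p × f, if undosed relapsers count as non-successes
- SE = √(p(1 − p)/m)

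| Relapse timing | R = 30% | R = 50% | R = 70% |
|---|---|---|---|
| Constant hazard (k = 1) | 24% | 21% | 16% |
| Falling hazard (k = 0.7) | 17% | 15% | 11% |
| Falling hazard (k = 0.5) | 12% | 11% | 8% |

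If relapses are uniform in time, f = 14/52 = 27%. The range is therefore about 8-27%. It covers the week-38 rule only; weight and pregnancy would add to it by an amount the documents do not allow one to estimate. Relapse must be confirmed by week 38, and the MADRS criterion needs two visits 5-14 days apart, so the effective limit is somewhat earlier. With week 36, the R = 50% constant-hazard figure becomes 24%.

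**Central case.** R = 50%, constant hazard, 50% response at Day 43, p = 0.60.

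- S(38) = 0.5^(38/52) = 0.603, so f = (0.603 − 0.5)/0.5 = 0.205.
- The RTS rate is 60%. The literal 2.5.1 rate is 0.60 × (1 − 0.205) = 47.7%, a shift of 12.3 points.
- All arms pooled: 195 × 0.5 × 0.5 ≈ 49 relapsers, of whom 49 × 0.795 ≈ 39 are retreated. SE = √(0.24/38.75) = 7.9 points, so the shift is 12.3/7.9 ≈ 1.56 SE.
- One full retreatment arm: 30 plus 30 × 2/11 ≈ 5.5 from placebo gives 35.5 participants, about 9 relapsers and 7 retreated. SE = √(0.24/7.05) = 18.4 points, so the shift is 12.3/18.4 ≈ 0.67 SE.

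**When the shift exceeds one SE.** The condition is m > (1 − p)/(p f²). At f = 0.20 this needs more than 25 retreated for p = 0.5, more than 16.7 for p = 0.6, and more than 6.2 for p = 0.8.

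**Grid.** Day 43 response 40-60%, R 30-70%, p 0.4-0.8 and k = 0.7 or 1 give 150 scenarios. The shift exceeds one SE in 110 with all arms pooled and in 9 for a single retreatment arm, where it is typically 0.4-0.9 SE.

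**The case against.** The two sections can be reconciled. The 2.5.1 sentence opens by placing itself after retreatment and speaks of meeting the criteria again, so it may mean retreated participants only. SAP 2.5.2 names the RTS outright, 2.1.3 assigns retreatment-period efficacy to the RTS, and grouping by the first retreatment infusion leaves an undosed relapser without a row. On that reading there is one denominator and the rate does not move. This is a fair reading and may well be the intent. But the sentence goes on to say all relapsing participants, no rule covers those never dosed, and the edit then only states what was meant.

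The consequence is also limited. SAP 2.5.2 tests no hypothesis on secondary efficacy endpoints and does not list this one for modelling. Protocol sections 12 and 12.7 base dose selection on data up to Day 57. SAP 2.1 adds time to relapse to the interim's focus, not retreatment success. Relapse to 12 months is reported for all responders and remitters, so late relapsers stay visible, and SAP 2.2.1 already lists reasons for exclusion from each analysis set. All of this stands and holds the severity down.

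The extra Table 5-2 criteria mostly restate who may be retreated. They matter only for someone retreated without meeting the criteria, and the documents give no basis for saying how often that would happen.

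**Conclusion.** SAP 2.5.1, taken literally, and SAP 2.5.2 give different denominators, and the protocol ensures that the two groups can differ. The direction is certain on the literal reading: the 2.5.1 rate is equal to or lower than the RTS rate. The central-case shift of about 12 points rests on assumed relapse, response and success rates, and on counting undosed relapsers as non-successes, which the SAP does not state.

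Three stronger inferences are not supported:

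- **That the week-38 rule bars a fifth of relapsers.** This follows from a constant hazard with about 50% relapse; other assumptions give about 8-27%.
- **That the reported rate moves by more than one standard error.** This is common only with all arms pooled, and the SAP names no pooled rate for this endpoint. By arm the shift is usually below one SE.
- **That a durable dose would be penalised in dose selection.** Selection does not use this endpoint. Any contrast between arms is also blurred, because placebo participants are reallocated to active arms and later relapsers move to the selected Phase 3 regimen.

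Severity is minor to moderate: the endpoint is descriptive, but the proportion is itself the reported result and its definition should not be left open.

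**What to change.** 1. In SAP 2.5.1, state that the denominator is all participants in the Retreatment Set, as in 2.5.2.
2. Beside the rate, report by arm the number of relapsing end-of-Core responders and remitters who were not retreated, with the reason: week 38 or later, weight, pregnancy, or other. Group them by assigned Core arm, since they have no retreatment arm.
3. In Table 5-2, keep only "No retreatment administered" as the RTS exclusion, to match 2.1.3. Every retreated participant then stays in the retreatment safety tables. The other two criteria can be flagged as deviations where a dosed participant did not meet them.

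The cost is SAP wording and one added set of counts. No new data are needed and no clinical rule changes. The edit should be made before the final analysis.
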